Research question: does an enhanced diagnostic workup for patients about to start empiric tuberculosis treatment in Lusaka, Zambia, lead to alternative diagnoses and improved patient outcomes after six months?

Primary objective: to determine in what proportion of patients who are about to start empiric tuberculosis treatment, an alternative diagnosis can be made through the use of a concise additional workup by an experienced pulmonary physician, including review of available data, as well as additional laboratory, functional, and imaging investigations

Secondary objectives: to determine whether establishing and treating alternative diagnoses in patients who were about to start empiric tuberculosis treatment leads to improved quality of life and survival after six months

In- and exclusion criteria: All adult patients who have a negative initial GeneXpert MTB/RIF test on sputum, but are about to start standard first-line treatment for suspected pulmonary tuberculosis on clinical grounds (i.e. empiric tuberculosis treatment), at four first-level Hospitals in Lusaka, Zambia. Patients will be excluded if they are inpatients (due to suspected tuberculosis).

Number of eligible patients per year: Estimated 410 eligible patients per year in Chawama (450 clinically diagnosed pulmonary tuberculosis patients at Chawama first-level hospital in 2023, including children). The total population at Chawama first-level hospital in 2023 included 5361 presumptive tuberculosis cases, of whom 5270 had GeneXpert MTB/RIF testing done, and of whom 426 had a positive result from GeneXpert MTB/RIF. There is a discrepancy with the number of bacteriologically confirmed tuberculosis cases, which is reported at 663 for the year. The reason for this is not entirely clear, but might be due to additional testing being performed at different facilities, and the use of other tests for diagnosing tuberculosis, such as lipoarabinomannan assay and acid-fast bacilli smear. Interestingly, the percentage of patients who had a tuberculosis relapse was higher in patients being treated empirically than in patients with bacteriologically confirmed tuberculosis (107 out of 450 (24%) versus 107 out of 663 (16%)).

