Treatment outcomes for 2022 are as follows: 618 bacteriologically confirmed new cases of which 523 were cured (85%), 29 completed treatment, 36 died (6%), 3 failed treatment, 24 were lost to follow up, and 3 were not evaluated; 123 bacteriologically confirmed tuberculosis relapses of which 115 were

cured (93%), 5 died (4%), 2 were lost to follow up, and 1 was not evaluated; 352 clinically diagnosed new cases of which 308 completed treatment (88%), 35 died (10%), 1 failed treatment, 7 were lost to follow up, and 1 was not evaluated; 156 clinically diagnosed tuberculosis relapses of which 143 completed treatment (92%), 9 died (6%), and 3 were lost to follow up.

The other first-level hospitals had somewhat lower numbers of patients in 2023.

Intervention: All included patients will undergo the study intervention. Participants will be included from the tuberculosis clinic at first-level hospitals. They will be reviewed by one of the study physicians prior to initiating empiric tuberculosis treatment. A full history and physical examination will be taken and available results will be reviewed (laboratory results, sputum results, and chest X-ray). Depending on the results, appropriate measures will be taken there, including possible treatment with antibiotics or a wait-and-see approach for suspected viral infections. If further diagnostics are deemed to be indicated, a patient will be referred to the pulmonology clinic at University Teaching Hospital in Lusaka, Zambia. There, appropriate additional diagnostics will be requested, including additional blood tests (such as aspergillus serology), repeat chest X-ray, spirometry, CT-scan of the chest (if no other clear clinical diagnosis), bronchoscopy (if indicated based on CT-scan) and sputum and/or bronchial washing bacterial and mycobacterial cultures. The empiric treatment will be withheld initially if the study investigator thinks that an alternative diagnosis is more likely, while awaiting the additional investigations. If the study investigator thinks it is in the interest of the patient, then empiric tuberculosis treatment will be initiated while awaiting the results for the additional investigations. When a final diagnosis is made, appropriate treatment decisions will be made. If a clear diagnosis cannot be made locally, patients will be discussed in a multidisciplinary team meeting between St. Antonius Hospital and University Teaching Hospital.

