Methods: Participants will be asked to participate in the study once the clinician at the first-level hospital has decided to start empiric tuberculosis treatment. If the patients provide written informed consent, they will be reviewed by the study physician on-site, and possibly referred for further investigations as described above. Quality of life will be assessed at baseline, as well as during follow up. Patients will be followed up for 6 months, at which time every patient file will be reviewed by a study investigator and the final diagnosis will be determined.

Primary outcome: diagnosis at 6 months (tuberculosis versus alternative diagnosis)

Secondary outcomes: quality of life at 6 months (EUROHIS-QOL), change in quality of life from baseline to 6 months (EUROHIS-QOL), survival at 6 months, number of patients that received tuberculosis treatment, number of patients that had side effects attributed to tuberculosis treatment,

Number of patients to include: 300

Sample size calculation: The power is set at 80% and α at 0.05. Assuming a 10% mortality in the historic control group (based on 2022 tuberculosis outcome data from Chawama first-level hospital), and a 5% mortality in the intervention group, 238 patients will have to be included. A safety margin of 20% of refusal to participate in the study and loss to follow up is assumed, so that approximately 300 patients will have to be included.

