Statistical analysis: Descriptive statistics will be used to describe percentage of alternative diagnoses, as well as percentage of patients that has quality of life scores indicating they are not satisfied or very dissatisfied, the percentage of patients who received tuberculosis treatment and the percentage of patients that had side effects attributed to tuberculosis treatment. Paired analyses will be used to compare quality of life at baseline and during follow up. Multivariate regression analyses will be used to identify what factors associate with quality of life and survival. We will use per-protocol analysis methods for the primary analyses, with intention-to-treat analyses as a secondary tool. We will use a historic control group of patients who underwent empiric TB treatment at the study sites in the year prior to the study as a comparison for survival. Additionally, as data for the tuberculosis clinic are collected in a standard fashion, it will be able to compare the number of patients being referred to the clinic, the number of patients receiving treatment for bacteriologically confirmed tuberculosis, and the number of patients receiving empiric tuberculosis treatment, as well as treatment outcome data, between the study period and the period prior to and after the study.

Burden and risks for participants: The burden for the participants consists of having to travel to University Teaching Hospital (4.2 km – 10.6 km distance) for review and potential additional investigations that cannot be done on the same day (CT-scan and bronchoscopy). The additional investigations might necessitate venepuncture (slightly painful, low risk of hematoma or bleeding), chest X-ray (low dose radiation (0.1mSv)), spirometry (low risk of feeling uncomfortable), and

potentially CT-scan of the chest (medium dose radiation (6.1 mSv)), and bronchoscopy (discomfort for most patients, risk of serious complications (e.g. bleeding, pulmonary oedema, pneumothorax) ca. 1%). It needs to be emphasized that these investigations would be considered as the standard-of-care in a high-resource setting, and, in that sense, are not actually an additional burden at all.

Study duration: 16 months

Start date: 1/12/2024

Final inclusion: 31/12/2025

End date: 30/06/2026

Dissemination plan:

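### The historic control for survival is not limited to adults or outpatients as the study cohort is, and no adjustment is tied to that comparison

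*Combined protocol and SAP*

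**What the plan says.** **Study cohort.** The In- and exclusion criteria admit adults with a negative initial sputum GeneXpert who are about to start treatment for suspected pulmonary tuberculosis on clinical grounds, at four hospitals. They add: "Patients will be excluded if they are inpatients (due to suspected tuberculosis"). Methods adds written consent. Every participant receives the intervention, so there is no concurrent control.

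**Control for survival.** The Statistical analysis section says: "We will use a historic control group of patients who underwent empiric TB treatment at the study sites in the year prior" to the study. It states no age limit, no inpatient exclusion and no start date for the controls' six months.

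**Regression.** The same section says: "Multivariate regression analyses will be used to identify what factors associate with quality of life and survival". It names no covariates and does not mention the controls.

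**Clinic-level comparison.** That section also plans to compare referrals, treatment counts and treatment outcomes at the clinic between the study period and the periods before and after it.

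**Sample size.** The calculation rests on mortality: "Assuming a 10% mortality in the historic control group (based on 2022 tuberculosis outcome data from Chawama first-level hospital), and a 5% mortality" among study patients.

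**Clinic counts.** The section on eligible patients per year estimates 410 eligible at Chawama from "450 clinically diagnosed pulmonary tuberculosis patients at Chawama first-level hospital in 2023, including children". For 2022 it reports "352 clinically diagnosed new cases of which 308 completed treatment (88%), 35 died (10%), 1 failed treatment, 7 were lost to follow up", with one more not evaluated, and "156 clinically diagnosed tuberculosis relapses of which 143 completed treatment (92%), 9 died (6%), and 3 were lost to follow up".

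**The concern.** The two groups in the survival comparison are not defined in the same way. Children and inpatients are kept out of the cohort, but nothing in the text keeps them out of the controls. If their mortality differs from that of eligible patients, the groups would differ even if the workup changed nothing. The one analysis that might correct for case mix is described as a search for associated factors, not as an adjusted comparison of study patients with controls. The way unknown outcomes are counted is also open in both groups.

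Survival is a secondary outcome, and the primary outcome, diagnosis at six months, does not use the controls. Still, survival is part of the research question and is the only outcome behind the sample size. As written, an observed mortality difference could not be separated from differences in who was counted and how.

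**Working it through.** **1. The plan's own figures.** Testing one proportion against a fixed 10%, two-sided 5%, 80% power:

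n = [1.96 × √(0.10 × 0.90) + 0.8416 × √(0.05 × 0.95)]² / 0.05² = 238.03, matching 238. Then 238 / 0.8 = 297.5, about 300.

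The 10% matches the 2022 Chawama new clinically diagnosed cases: 35/352 = 9.9%. With relapses included it is (35 + 9)/(352 + 156) = 44/508 = 8.7%. The calculation treats the control rate as known, so it makes no allowance for how the control group is assembled.

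**2. The definitions side by side.**

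| Feature | Study cohort | Historic control |
|---|---|---|
| Adult | required | not stated |
| Inpatient for suspected tuberculosis | excluded | not stated |
| GeneXpert-negative, pulmonary | required | arguably implied, because the eligibility text equates such treatment with empiric treatment |
| Consent | required | no equivalent |
| Entry | decision to treat | underwent treatment |
| Sites | four hospitals | study sites |

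**3. How many might not qualify.** At Chawama in 2023: (450 − 410)/450 = 40/450 = 8.9%. The wording points to children. Whether the 410 also leaves out inpatients is not said. The documents give no mortality by age or inpatient status, so no bias can be calculated from this share.

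**4. New versus relapse, the one case-mix factor with data.** Relapses are eligible, so this tests drift in case mix and is not an eligibility mismatch.

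- Mortality in 2022: new 35/352 = 9.9%, relapse 9/156 = 5.8%; difference 4.2 points (95% CI −0.6 to 9.0, p = 0.12).
- Relapse share: 156/508 = 30.7% in 2022, 107/450 = 23.8% in 2023.
- Expected mortality at each share: 0.693 × 9.94% + 0.307 × 5.77% = 8.7%, and 0.762 × 9.94% + 0.238 × 5.77% = 9.0%.

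Exact enumeration with no intervention effect (238 study patients, 508 controls, pooled z test, two-sided 5%):

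| Relapse share | False benefit | False harm |
|---|---|---|
| Equal in both groups | 2.2% | 2.7% |
| Control 23.8%, study 30.7% | 3.0% | 2.0% |
| Control 30.7%, study 23.8% | 1.7% | 3.7% |

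A shift of this size has little effect.

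**5. Unknown outcomes.** Chawama 2022: 7 + 3 = 10 lost, 1 not evaluated, and 1 relapse not listed (143 + 9 + 3 = 155, not 156). Total 12/508 = 2.4%. The last column sets each control rate against an illustrative study result at the planned effect, 12/238 = 5.0% with complete follow-up (pooled z, two-sided).

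| Rule for the 12 | Control mortality | p |
|---|---|---|
| Counted alive | 44/508 = 8.7% | 0.080 |
| Excluded | 44/496 = 8.9% | 0.067 |
| All counted dead | 56/508 = 11.0% | 0.008 |

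The extreme spread is 12/508 = 2.4 points, against the 5-point difference that sized the trial. These are 2022 figures from one hospital, and the 2022 cases are not labelled pulmonary. The planned control is all study sites in the year before a December 2024 start.

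**The case against.** The plan declares its historic control openly and does limit it, by treatment, sites and year. The eligibility text can be read as carrying GeneXpert-negative pulmonary disease into the term empiric treatment. A reader might infer that the control has no eligibility limits at all; the documents do not support that. What is missing is age and inpatient status.

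The investigators also know that their clinic counts include ineligible patients, since they reduced 450 to 410. They may intend the same for the controls, but the analysis text does not say so.

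The before-and-after comparison of treatment outcomes uses the same clinic population in each period, so the age and inpatient mismatch does not arise there. That stands as far as it goes. But it describes treated clinic patients by period, while study patients may have treatment withheld, so it does not replace a comparison for the study cohort.

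The figures that come from the documents are modest. The relapse shift matters little, the two ordinary ways of handling unknown outcomes differ by 0.2 points, and the 11.0% requires all 12 to have died, including one who may be a reporting slip. Usual treatment lasts six months, so end-of-treatment outcomes roughly match six-month follow-up. All of this stands and limits the weight of the point. Nor can filtering and adjustment remove calendar-time or consent differences.

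**Conclusion.** The point holds as a cheap improvement, not a demonstrated error. Followed as written, the plan compares a selected cohort, without adjustment, with controls who are not limited to adults or outpatients, on the outcome that sized the trial. The primary outcome is unaffected.

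A reader might infer that the control is built to favour the intervention. The documents do not support that: including children could lower control mortality, including inpatients could raise it, and neither effect can be sized. No inpatient share or inpatient mortality is given, so any figure for false benefit from that source would be invented.

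The documents do support a share of about 9% not eligible at Chawama, if the 410 reflects the study criteria. They also support a control rate of 8.7% to 8.9% under ordinary counting rules, and 11.0% at the extreme, if 2022 Chawama resembles the control year and sites. The rules for unknown outcomes and start date would be closer to missing detail on their own; restriction and adjustment are the substance.

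**What to change.** Amend the Statistical analysis section, before outcomes are compared:

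1. Restrict historic controls, as far as register fields allow, to adults who were not inpatients at the treatment decision, with suspected pulmonary tuberculosis and no positive GeneXpert, at the same four sites. Do not demand a documented negative result: the protocol says a discrepancy in its own counts "might be due to additional testing being performed at different facilities", so a result may not be on file.
2. Make the main survival comparison a model of study versus control, adjusted for variables recorded in both groups: at least site and new versus relapse, plus age, sex and HIV status if recorded.
3. Treat unknown outcomes the same way in both groups, with best-case and worst-case bounds, and count six months from the nearest matching date.
4. Keep the unrestricted, unadjusted comparison as a sensitivity analysis, and state that calendar-time and consent differences remain.

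The cost is a few sentences, a check of register fields, a filter and one model. Enrolment and procedures do not change. The downside is a smaller control group and possibly missing fields. If only aggregate outcomes exist, stratify by site and new versus relapse and show the bounds.

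### The survival comparison with the historic group has no common time zero or death window, so part of any mortality difference may come from the measure

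*Combined protocol and SAP*

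**What the plan says.** **Study cohort.** Under Methods, patients are approached once the first-level clinician has decided on empiric treatment. Under Intervention, the study physician sees them before that treatment begins, and for some it does not begin then: "The empiric treatment will be withheld initially if the study investigator thinks that an alternative diagnosis is more likely". Survival at six months is a secondary outcome. Methods gives the length of follow-up, "Patients will be followed up for 6 months, at which time every patient file will be reviewed by a study investigator", but not the date from which the six months run. Entry to the study is the natural reading.

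**Historic group.** Statistical analysis says: "We will use a historic control group of patients who underwent empiric TB treatment at the study sites in the year prior to the study", to serve as the comparison for survival. It names no time zero, no window and no rule for what counts as a death.

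**The only historic mortality shown.** The 2022 treatment outcomes, listed after the number of eligible patients, sort each patient into one category: cured or completed, died, failed, lost, or not evaluated. Among 352 clinically diagnosed new cases, 35 died. The Sample size calculation draws on these data: "Assuming a 10% mortality in the historic control group (based on 2022 tuberculosis outcome data from Chawama first-level hospital".

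**Course length.** Background and justification gives a usual treatment duration of six months.

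**The concern.** A comparison of survival between two groups needs the same starting event and the same time at risk in both. This plan fixes neither, and the information it gives points to two possible mismatches.

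- **Start.** A death between the decision to treat and the first dose can count in the study cohort. It cannot appear in a group defined by having undergone treatment. If risk is highest in the first weeks, this makes historic mortality look lower and works against the intervention.
- **End.** A treatment-outcome category closes when the course closes. Courses that run past six months add deaths to the historic count, which favours the intervention. Courses that end early remove deaths, which works against it.

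Using programme outcomes on both sides would not solve this, because participants who are never treated have no course outcome.

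Survival is a secondary outcome, but the 10% versus 5% mortality contrast sets the sample size. A shift in the historic rate caused by measurement alone would feed straight into the conclusion.

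**Working it through.** **1. The plan's own figure.** Inputs from the Sample size calculation: "The power is set at 80% and α at 0.05"; historic mortality 10%; "a 5% mortality in the intervention group, 238 patients will have to be included". A two-sided one-sample test against a fixed 10% gives

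n = (1.960·√(0.10·0.90) + 0.842·√(0.05·0.95))² / 0.05² = 238.03.

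This matches 238. The 20% margin gives 238/0.80 = 297.5, so 298, which matches approximately 300. The usual two-group formula gives 435 per group and does not match. The stated number is therefore reproduced when the historic 10% is treated as a known constant, and any measurement shift in that 10% passes undiluted into the test.

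**2. The historic 10%.** 35/352 = 9.9%. The denominator includes 7 patients lost to follow-up and 1 not evaluated. If all 8 had died, the rate would be 43/352 = 12.2%. Unknown vital status alone spans about 2.3 points.

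**3. Sensitivity to window length.** The documents give no actual course lengths, so this step rests on three assumptions: constant hazard, no true effect of the work-up, and a historic 10% accrued over T months on average. The study's six-month mortality is then 1 - 0.9^(6/T), and the artefact is 10% minus that rate. The last column uses n = 238 and the lower rejection limit 0.10 - 1.96·√(0.09/238) = 0.0619. It gives the normal-approximation chance that the study proportion falls below that limit.

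| T (months) | Study six-month rate | Artefact (points) | Chance of falsely declaring benefit |
|---|---|---|---|
| 5 | 11.9% | -1.9 | 0.3% |
| 5.5 | 10.9% | -0.9 | 1.0% |
| 6 | 10.0% | 0 | 2.5% |
| 6.5 | 9.3% | +0.7 | 5.1% |
| 7 | 8.6% | +1.4 | 9.0% |
| 8 | 7.6% | +2.4 | 20.6% |

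A positive artefact favours the intervention. At the nominal six months it is zero.

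**4. If only some courses run long.** As an illustration, suppose one course in ten lasts eight months and the rest six. The six-month rate p then solves 0.9p + 0.1·[1 - (1 - p)^(8/6)] = 0.10, so p ≈ 9.7% and the artefact is about 0.3 points. The ends of the table need the average course to depart from six months by one to two months.

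**5. The start mismatch.** Under constant hazard, moving a six-month window later leaves six-month mortality unchanged. This mismatch matters only if risk is uneven over time, and the documents give nothing on early mortality. No figure can be attached to it.

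**The case against.** The strongest reply is that the mismatch is inferred. The plan does not say that the historic comparison will use the programme's *died* category. The 10% is a planning figure from one hospital in 2022, whereas the comparator is the year before the study at all study sites. No section defines *died* as death during a course. With a usual course of six months, the two windows have the same nominal length. All of this stands. It rules out saying that part of any difference does come from the measure; the text supports only that it may.

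Three stronger readings are tempting and are not supported.

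- A reader might infer that prolonged courses account for a large share of the planned 5 points. That needs the average historic course to run well beyond six months, and the documents do not show it.
- A reader might infer a fixed loss of deaths for each week between decision and first dose. Under constant hazard a later start changes nothing. Only a shorter window would.
- A reader might infer that this is the only comparison of outcome between groups. Statistical analysis also compares programme treatment outcomes between the study period and the periods before and after it. That comparison uses routinely collected clinic data throughout, but participants who were never treated have no treatment outcome to contribute.

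The reply does not remove the gap. A window that is undefined rather than different still has to be defined before historic data are extracted. The restriction of the historic group to treated patients is explicit in the text.

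**Conclusion.** The point holds in a limited form. The plan sets no common time zero or death window for its survival comparison. Study patients enter before treatment and may never receive it, whereas historic patients are included because they received it. The only mortality shown for such patients is an end-of-course category. A measured difference may therefore partly reflect the way deaths are counted.

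Size and direction cannot be determined from the documents. The length artefact is zero at the nominal six-month course. It runs from about -1.9 to +2.4 points, against a planned 5, only under the assumption that the 10% accrued at constant hazard over an average of 5 to 8 months. The start mismatch works against the intervention if early risk is high, and long courses favour it. This is an avoidable weakness in a secondary outcome that drives the sample size, and it is worth correcting before historic data are extracted.

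**What to change.** In Secondary outcomes and Statistical analysis:

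- Define survival in both groups as death from any cause within 183 days of the closest equivalent date available in both. This is the decision to treat or, if the registers hold nothing earlier, register entry or treatment start.
- Take individual start and death dates for historic patients, and do not use the end-of-course *died* category.
- Count no death after day 183 in either group.
- Report bounds, from all alive to all dead, for patients whose vital status at day 183 or date of death is unknown.
- If only treatment-start dates exist historically, state that pre-treatment deaths are missing from that group, and report study deaths before treatment start separately.

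The cost is protocol wording and date extraction from the site registers. The documents do not show that the registers hold death dates, so some will be missing and the bounds may be wide. No extra patients or visits are needed. The stated final inclusion (31/12/2025) and end date (30/06/2026) are 181 days apart, so a 183-day window needs the end date moved by two days for the last patient.

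### The survival comparison with prior-year patients from the same four hospitals specifies no stratification or adjustment by hospital, so a shift in hospital mix could confound it

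*Combined protocol and SAP*

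**What the plan says.** - **Sites.** Under In- and exclusion criteria, patients are recruited "at four first-level Hospitals in Lusaka, Zambia". Number of eligible patients per year gives detailed counts for Chawama only. Of the rest it says: "The other first-level hospitals had somewhat lower numbers of patients in 2023".
- **Comparison.** Statistical analysis states: "We will use a historic control group of patients who underwent empiric TB treatment at the study sites in the year prior to the study". It gives no test, model, stratification, adjustment or standardisation for this comparison. A multivariate regression for factors associated with survival is planned, but neither hospital nor the historic group is mentioned in connection with it.
- **Size.** Sample size calculation sets 80% power and α 0.05. Its control rate comes from one hospital: "Assuming a 10% mortality in the historic control group (based on 2022 tuberculosis outcome data from Chawama first-level hospital". Against this it sets 5% mortality under the work-up and arrives at 238 patients. To cover losses it then says: "A safety margin of 20% of refusal to participate in the study and loss to follow up is assumed". The enrolment line reads: "Number of patients to include: 300". The 300 are not divided among the hospitals.
- **Status.** Survival at six months is a secondary outcome, but it is the outcome on which the sample size rests. The primary outcome, diagnosis at six months, is analysed descriptively with no historic comparison.

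**The concern.** The historic group will reflect each hospital's routine volume. The study group will reflect where the study physicians recruit. If the two mixes differ and the hospitals differ in mortality, part of any before/after difference is a difference between hospitals and not an effect of the work-up. The error can run in either direction.

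Survival is one of the two patient outcomes in the secondary objective. Without randomisation, protection against known confounders has to come from the analysis, and hospital is a confounder the design already lets the analyst control, because every hospital contributes to both periods. Leaving the method open also means that a crude and a stratified result could both be produced and one chosen after the data are seen.

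**Working it through.** **1. The plan's own figure.** Inputs from Sample size calculation: 10% versus 5%, α 0.05 (taken as two-sided), power 80%. A one-sample test against a fixed rate gives

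n = [1.960·√(0.10·0.90) + 0.842·√(0.05·0.95)]² / 0.05² = 238.03,

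and 238/0.80 = 297.5, about 300. The plan's figure is reproduced. The formula contains no hospital term and treats the 10% as known without error. The 10% matches new clinically diagnosed cases at Chawama in 2022 (35/352 = 9.9%). With relapses included it is (35 + 9)/(352 + 156) = 44/508 = 8.7%.

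**2. Shift from mix alone.** Assumed controls: 410 at Chawama (the plan's annual estimate of eligible patients) and 287 at each other hospital (70% of 410), total 1,271. Chawama's share is 410/1,271 = 32.3%. Assumed mortality: 8.7% at Chawama and 5% elsewhere, no treatment effect. The false difference is (study share − 0.323) × 3.7 points:
- 10% from Chawama: −0.223 × 3.7 = −0.8 points
- 80% from Chawama: +0.477 × 3.7 = +1.8 points

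In general the shift cannot exceed the share of patients moved between hospitals times the range of hospital mortality. Producing the full 5 points would take, for example, a 50% shift and a 10-point range.

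**3. False-positive rate.** Simulation, 40,000 null trials per cell: logit-normal hospital mortality with mean 10%, unchanged between periods; 238 study patients; the 1,271 controls above; two-sided 5% test. The remaining study patients are split equally over the other three hospitals.

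| Study mix | Crude, SD 3 points | Crude, SD 4 points |
|---|---|---|
| Proportional to controls | 5.0% | 4.9% |
| Equal | 5.0% | 5.1% |
| Half from Chawama | 5.8% | 6.3% |
| 10% from Chawama | 6.4% | 7.4% |
| 80% from Chawama | 11.4% | 16.1% |

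The hospital-stratified Mantel-Haenszel test stayed at 4.8–5.1% in every cell. With mean mortality 8.7% the crude rates were within about one percentage point of these.

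**4. Price of stratifying.** With common mortality, the crude variance is proportional to 1/238 + 1/1,271 = 0.00499. The Mantel-Haenszel variance is proportional to 1/Σ[n₁n₀/(n₁+n₀)]. At 80% from Chawama the sum is 190.4·410/600.4 + 3·(15.87·287/302.87) = 175.1, giving 0.00571. The ratio is 1.14, so the standard error rises by a factor of 1.07. For moderate mixes the increase is negligible.

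**5. What stratifying leaves.** Suppose each hospital's mortality also varies independently in each period with SD s. With four equally weighted hospitals this adds 2s²/4 to the variance. Against 0.09·(1/238 + 1/1,000) = 0.000468 (1,000 controls assumed), s = 1 point multiplies the variance by 1.107 and s = 2 points by 1.427. The two-sided error becomes 2[1 − Φ(1.96/√1.107)] = 6% and 2[1 − Φ(1.96/√1.427)] = 10%.

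**6. Power against a real historic sample.** For the pooled-variance test, with 1,271 controls: pooled rate (11.9 + 127.1)/1,509 = 0.0921; null SE 0.0204; alternative SE 0.0164; power = Φ[(0.05 − 1.96·0.0204)/0.0164] = 73%. Depending on the approximation, power is about 65–66% with 508 controls, 71–72% with 1,000 and 73–74% with 1,271. Control numbers are assumed. An unpooled-variance test would give higher nominal power, but the matching one-sample size would then be (1.960 + 0.842)²·0.0475/0.0025 = 149, so it is not the test behind 238.

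**The case against.** The strongest reply is that the plan chooses no wrong method; it is silent. A reader might infer that patients are to be pooled and compared crudely. The text does not say so, and the planned regression could include hospital. That much stands: the defect is an unspecified analysis. It does not dispose of the point, because the regression is described as a search for associated factors and is not linked to the historic group.

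Second, the bias needs unequal hospital mortality and a shifted mix together, and the documents show neither. This also stands. Under proportional or equal recruitment the crude test is sound.

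Third, a reader could reach far more alarming figures. An intraclass correlation of 0.05 on the probability scale, with 80% of patients from Chawama, gives a crude false-positive rate of around 33%. That implies a between-hospital SD of √(0.05·0.10·0.90) = 6.7 points, larger than the planned effect, among four hospitals of the same level in one city. Nothing in the documents supports that spread or that mix.

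Fourth, confounding by mix should not be merged with non-independence of patients within hospitals. Stable hospital differences cancel in a within-hospital comparison. Only hospital-specific change between years remains, and stratifying does not cure it.

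**Conclusion.** The point holds as a gap in specification, with a moderate and conditional effect. The same hospitals supply both groups, no hospital adjustment is stated and no enrolment per hospital is set. Under the assumed SD of 3 to 4 points, moderate mixes bring the crude error to about 5–8%, and an extreme mix to 11–16%. In the worked example the distortion stays below 2 points. Hospital mortality, control numbers and study mix are all assumptions, because the plan gives none of them for all four sites. The primary outcome is unaffected.

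It would be wrong to conclude that 80% power fails only if hospitals drift between years. It falls short on the pooled test even without any hospital variation, because 238 treats the historic rate as fixed. Nor does the plan hide that the 10% comes from Chawama; Sample size calculation says so.

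**What to change.** In Statistical analysis, state that the secondary survival comparison uses a Mantel-Haenszel risk difference stratified by the four hospitals, or a regression with period and hospital as fixed effects. Report patients and deaths by hospital and period beside it, so that a result driven by one hospital is visible. State as a limitation that hospital-specific changes in mortality between years are not removed.

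If Sample size calculation is edited, say that 238 treats the 10% as a fixed known rate and give the power for the expected number of historic controls.

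The cost is wording. Controls are defined by study site, so hospital should be known for every patient in both periods. The only statistical price is a slightly larger standard error if recruitment is very uneven.
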